2. To validate these biomarkers and calculate the sensitivity, specificity, positive and negative predictive values for the detection of significant hepatic fibrosis compared to liver biopsy (the current gold standard).
3. To compare proteomic profiles in HIV-HCV co-infected and HCV mono-infected controls at similar fibrosis stages to determine if protein profiles are expressed differently.
4. To compare serum biomarkers with ongoing immunologic and non-invasive marker studies.

VI. METHODS

We will use a variety of methods to identify candidate biomarkers that could be 1) predictive of hepatic fibrosis, 2) sensitive to change over time and with exposure to therapeutic interventions, such as HAART, and HCV therapy and 3) potentially informative about the pathogenesis of HCV disease, particularly in the setting of HIV infection. The current proposal forms one of the key elements in a broader research program aimed at identifying markers of fibrosis. Concurrent projects will evaluate immunologic, serologic and radiologic markers (and are/will be funded separately). The novel aspect of the current proposal is the serum proteomics biomarker discovery effort that will be conducted in collaboration with Drs. [name] and [name].

Our overall approach for biomarker discovery will proceed step-wise with selection of well-defined controls at each step (Fig. 1). As multiple aliquots of serum and plasma are made at each patient visit, we will be able to evaluate each candidate biomarker in parallel, permitting comparative analyses and assessment of their utility alone and in combination. Furthermore, as PBMC aliquots are similarly stored, comparisons can be made with ongoing immunologic studies at the same time points.

Figure 1. Proposed overall schema for discovery and validation of potential biomarkers.

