sera per fibrosis category and diagnostic group (total= 40 patients). In addition to simple across-group and across-category comparisons (ANOVA), correlations between the degree of fibrosis (biopsy scores) and individual biomarker peak intensities will be analyzed by Spearman rank-order correlation. Analyses according to fibrosis stage will be made overall and stratified by HCV-HIV co-infection status. Individual biomarkers that make unusually large contributions to the CART algorithms generated will be targeted for identification at this stage. We will focus on optimal samples for discovery and validation work. Once candidate biomarkers have been validated and identified, we will test intentionally ‘mishandled’ (e.g., repeated freeze-thaw) to assess the robustness of the each biomarker.

SELDI Data Analysis–Validation Larger numbers of sera will be separated by fibrosis category: minimal fibrosis (F0-1), mild fibrosis (F2), moderate fibrosis (F3), severe fibrosis/cirrhosis (F4) to assess the discriminatory ability of the individual biomarkers or biomarker patterns (n = 50-100 per fibrosis category and infection group). Ideally, equal numbers of patients will be studied in each of these groups. Although it may be more difficult to recruit individuals at the extremes (F0-1, F4), we observed the following distribution of fibrosis scores: 13 (28%) with F0-F1; 14 (35%) with F2, 10 (22%) with F3 and 9 (20%) with F4 among the 46 patients evaluated in our APRI validation study[47]. These data suggest that we should have a fair distribution across stages of fibrosis. If we find that scores are not evenly distributed, we may regroup stages to achieve groups of comparable sizes for analysis. The intensities of individual biomarker peaks and biomarker profiles will be compared within and between mono-infected and co-infected subjects as outlined above. All biomarkers making important contributions to distinguishing between groups and/or fibrosis categories will be confirmed by MALDI TOF MS and identified using a range of immunologic and mass spectrometric techniques (e.g.: EIAs when commercial kits exist or can be built easily, immunoprecipitation, Edmond sequencing, MS/MS).

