samples). It is in **Phase 3** studies that findings can be further validated through extensive analysis with other sample sets or control groups in addition to protein/peptide identification.

Feasibility Of 424 patients currently enrolled in the CCC, 53% are on HAART (with HIV RNA<50 copies/ml and CD4> 350) of whom 20% have undergone liver biopsy. Thus, we presently have sufficient samples to conduct Phase 1 studies in the co-infected. The full cohort is actively recruiting and is expected to reach its target by December 2008. Extrapolating from the currently enrolled patients, we expect 150-200 eligible subjects available for study. HCV mono-infected will be recruited retrospectively (through database review) and prospectively through the RVH HCV clinics which perform on average \approx 175 biopsies/yr. Thus the number of samples we require represents about 40% of available patients.

General Data Analyses Assessment parameters for the accuracy of proteomic biomarkers for the detection of significant hepatic fibrosis and cirrhosis will be calculated as shown in the simplified example in the table below. SAS PROC LOGISTIC (V.8.02; SAS Institute, Cary, NC) will be used to calculate AUROCs. Standard errors for the AUROC will be calculated according to Hanley and McNeil.[91] Primary analyses will group HIV co-infected and mono-infected subjects together according to level of fibrosis. We will also calculate the parameters for HIV co-infected and mono-infected separately. In addition, we will analyze promising candidate biomarkers combined with other markers of fibrosis that we are studying in parallel ongoing projects (e.g. HA, SHATA, APRI etc.).

Table 1. Diagnostic characteristics comparing proteomic biomarkers with liver biopsy scores

		Stage of HCV on Liver Biopsy	
		No Fibrosis/No Cirrhosis	Significant Fibrosis/cirrhosis
Proteomic biomarker	+	a (true positive)	b (false positive)
	-	c (false negative)	d (true negative)

Sensitivity = $a/a+c$; Specificity = $d/b+d$; Positive predictive value = $a/a+b$; Negative predictive value = $d/c+d$

IX. ROLES OF THE INVESTIGATORS

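### PPV and NPV are to be read as raw cell ratios from a pooled sample selected on biopsy stage, so they reflect the sampling mix to the extent that the stage and infection-group quotas are met

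*Protocol*

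**What the plan says.** Specific Aim 2 in the Protocol's Objectives (Section V) is to "calculate the sensitivity, specificity, positive and negative predictive values for the detection of significant hepatic fibrosis compared to liver biopsy". Under General Data Analyses (Section VIII), the accuracy parameters for significant fibrosis and for cirrhosis "will be calculated as shown in the simplified example in the table below". The line beneath Table 1 defines PPV as a over a plus b and NPV as d over c plus d. It contains no prevalence term, no weighting and no target population. The same section makes the pooled co-infected and mono-infected sample the primary analysis, with separate estimates by infection group as well.

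Under Patient Selection, subjects are chosen by the local pathologist's fibrosis score. Under SELDI Data Analysis–Validation, the target is "n = 50-100 per fibrosis category and infection group", across F0-1, F2, F3 and F4, with this aim: "Ideally, equal numbers of patients will be studied in each of these groups". If the stages turn out uneven, "we may regroup stages to achieve groups of comparable sizes for analysis". That section also gives an observed stage distribution in a 46-patient validation series for the APRI marker, but does not link it to the predictive values.

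**The concern.** Sensitivity and specificity are conditional on disease status. PPV and NPV are conditional on the test result, and so depend on how many diseased and non-diseased subjects the sample holds. When subjects are picked by the reference result, the investigators set that balance, and the raw cell ratios carry it into the reported PPV and NPV.

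Two balances are set here. The first is the stage mix: four equal stages put 75% of subjects at F2 or above, 50% at F3 or above and 25% at F4, whatever the source population looks like. The second is the ratio of co-infected to mono-infected subjects in the pooled primary analysis, which the quota per infection group also sets.

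At stake is how a stated aim is read. The Conclusions list less need for biopsy among the potential benefits of reliable biomarkers, and PPV and NPV are the figures a reader would use to judge that.

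**Working it through.** **Inputs**
- Stage counts in the 46-patient series (SELDI Data Analysis–Validation): 13, 14, 10 and 9 for F0-1, F2, F3 and F4. This is a co-infected series.
- Equal-stage target (same section): 25% per stage.
- Sensitivity (Se) and specificity (Sp) both 0.89. These are borrowed for illustration from the hepatitis B SELDI study described in the Protocol's review of earlier work, where they refer to significant fibrosis. Applying them at every cut-off in HCV is an assumption.
- A 10% prevalence, also an assumption. The Protocol gives no prevalence for unbiopsied patients.
- Cells a to d are read by their labels in Table 1 (true positive, false positive, false negative, true negative).

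**Step 1: the Protocol's own distribution.** The counts sum to 46. The shares are 13/46 = 28.3%, 14/46 = 30.4%, 10/46 = 21.7% and 9/46 = 19.6%. The printed share for F2 is 35%, and the four printed shares sum to 105%. The counts are therefore used: F2 or above 33/46 = 71.7%, F3 or above 19/46 = 41.3%, F4 9/46 = 19.6%.

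**Step 2: formulas.** With p the share diseased in the sample, the raw cell ratios tend to
- PPV = Se·p / [Se·p + (1 − Sp)(1 − p)]
- NPV = Sp(1 − p) / [Sp(1 − p) + (1 − Se)p]

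Example, F4 with equal stages (p = 0.25): PPV = 0.2225 / (0.2225 + 0.0825) = 73.0%; NPV = 0.6675 / (0.6675 + 0.0275) = 96.0%.

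Example, F4 with the 46-patient mix (p = 0.196): PPV = 0.1741 / (0.1741 + 0.0885) = 66.3%; NPV = 0.7159 / (0.7159 + 0.0215) = 97.1%.

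**Step 3: results**

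| Cut-off | p, equal stages | PPV / NPV | p, 46-patient series | PPV / NPV |
|---|---|---|---|---|
| F2 or above | 75% | 96.0% / 73.0% | 71.7% | 95.4% / 76.1% |
| F3 or above | 50% | 89.0% / 89.0% | 41.3% | 85.1% / 92.0% |
| F4 | 25% | 73.0% / 96.0% | 19.6% | 66.3% / 97.1% |

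At an assumed p = 10%: PPV = 0.089 / (0.089 + 0.099) = 47.3%; NPV = 0.801 / (0.801 + 0.011) = 98.6%.

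**Step 4: precision of the comparison series.** A chi-square test of 13/14/10/9 against equal stages gives 17/11.5 = 1.48 on 3 df (p = 0.69). Exact 95% intervals are 57–84% for F2 or above, 27–57% for F3 or above and 9–34% for F4. Each contains the equal-stage share.

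**Step 5: sensitivity.** Once stages are dichotomised, sensitivity also averages over the stage mix. With assumed detection of 60%, 80% and 95% in F2, F3 and F4, sensitivity for F2 or above is (60 + 80 + 95)/3 = 78.3% under equal stages, and (14×60 + 10×80 + 9×95)/33 = 75.6% under the 14/10/9 mix.

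**The case against.** The strongest reply is that equal numbers are only an ideal. The Feasibility paragraph expects 150-200 eligible co-infected subjects, while four stages of 50 already need 200. There is little or no surplus from which to impose equal stages, so the co-infected sample may be close to all eligible biopsied patients. This stands, and it limits the problem in that group. Quotas are more feasible in the mono-infected group, where the clinics perform about 175 biopsies a year, and the pooled mix of the two groups is still a product of recruitment targets.

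The regrouping fallback might be read as another way of fixing prevalence, so that two equal halves would give a PPV of 0.89 whatever the true prevalence. The Protocol does not support that. Merging stage categories discards nobody and leaves the share at or above a given stage unchanged.

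The large shifts rest on assumed prevalences, and the 46-patient series cannot be told apart from equal stages. Both points stand. The documented contrast is modest and is smallest at F2 or above.

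It can also be said that Table 1 is only a simplified example and that standardisation is analysis detail. This carries less weight. The text says that the parameters will be calculated as the table shows, so the calculation is stated and not left open.

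**Conclusion.** The point holds as a moderate one. The Protocol commits to PPV and NPV, fixes them as raw cell ratios, and applies them to a pooled sample chosen on the reference result. To the extent that the quotas are met, the reported values follow the sampling mix.

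Against the 46-patient series, and with Se = Sp = 0.89, PPV would be overstated by 0.6 points at F2 or above, 3.9 at F3 or above and 6.7 at F4. NPV would be understated by 3.1, 3.0 and 1.1 points (differences taken from the rounded values in the table). Larger gaps appear only at prevalences that the Protocol does not give.

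A reader might infer that the predictive values describe no patient population at all, or that standardising makes every result look worse. Neither follows. The co-infected sample may lie near the biopsied case mix, and NPV, the figure that bears on ruling out fibrosis, rises at every cut-off when prevalence is below the sample share. Sensitivity and specificity are affected only through the stage mix within each class.

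**What to change.** In General Data Analyses:

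- Make sensitivity, specificity and AUROC the main accuracy results, and report the marker-positive proportion for each fibrosis stage.
- Do not report a/(a+b) and d/(c+d) from the stage-selected sample as PPV and NPV.
- Obtain PPV and NPV by Bayes' rule, separately by infection group, at the stage distribution of all biopsied patients in that group's source: the cohort database for the co-infected and the hospital HCV clinics for the mono-infected. Also show them over a stated prevalence range.
- Use the 46-patient series, by its counts, only to illustrate the co-infected group. It is too small to be the sole source of weights and cannot supply weights for the mono-infected.

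The cost is a little more analysis and a tabulation of stages among all biopsied patients in each source, with no new samples or assays. Reported PPV will be somewhat lower wherever true prevalence is below the sample share.

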General Methods for Proteomic Analysis using SELDI-TOF MS. [see schema: Figure 2, attached] Quantitative proteomic profiles will be obtained using standard methods.[80] All samples will be analyzed without knowledge of the fibrosis stages [essentially as outlined in Manuscript #3]. Briefly, samples will be thawed on ice at the time of profiling, denatured with 9M urea and fractionated using a range of methodologies. The first ‘pass’ will typically involve column fractionation with a series of four extraction buffers (pH 9 – organic) and binding to at least two chip chemistries; weak cation exchange (CH10) and immobilized metal affinity capture (IMAC; CIPHERGEN Biosystems, Fremont CA). At least two different matrices will be applied and spectra will be generated using high- and low-laser intensity (i.e., targeting larger vs. smaller proteins, respectively). Standard QA and AC procedures will be followed throughout. The protein chip arrays will be analyzed using the SELDI PCS4000 Enterprise System (BioRad) normalized using total ion current. Peak clustering will initially be assessed using Biomarker Wizard Software (Vermillion Inc.) at settings that provide a 5% minimum peak threshold, 0.2% mass window, and 2% to 3% signal/noise determination. Intensity values for each peak will be averaged for each duplicate sample pair analyzed and input into BioMarker Patterns software (Vermillion) for classification tree analysis. This decision-analysis software uses a proportion of the generated database to combine these individual biomarkers to achieve the greatest sensitivity and specificity. Using Classification and Regression Trees, multiple biomarkers are correlated with specific phenotypes to improve sensitivity and specificity over single markers. The output is an easy-to-interpret decision tree, using a small panel of markers with defined splitting rules. Each such decision tree represents a potential, 1st generation diagnostic test (a SELDI platform-based assay). The approach outlined above focuses on the identification of potential biomarkers among the higher-abundance proteins and/or their metabolic byproducts (e.g., abnormally synthesized or truncated host proteins). Although the IMAC and CH10 chips typically yield the greatest number of interesting biomarkers, pooled sera from the groups will also be screened over a wider pH range and using additional chip (fractionation) chemistries such as hydrophobic binding (H50), high glycoprotein binding (gadolinium-buffered IMAC) and strong anionic binding (SAX). Any promising candidate biomarkers observed in these parallel screens of pooled serum will be confirmed using individual samples.

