Justification for sample size Much of the published protein profiling work does not meet minimal standards for sample size. Although sample size considerations are critical, the process of defining ‘adequate’ can be difficult when no prior knowledge exists about the proteins under study. While standard sample size calculations can be applied, none works particularly well in the context of proteomic profiling because so little is known *a priori* about the complexity of the final model before an experiment is completed, or about the individual biomarkers that will be included in that model.[89, 90] This is why biomarker studies are typically divided into three phases. In **Phase 1 (Discovery)**, small numbers of specimens (~10 cases/controls) are subjected to extensive fractionation across multiple chip chemistries and conditions to optimize the detection of discriminatory proteins/peptides. In this phase, the focus is on sensitivity and stringency is typically low. **Phase 2 (Validation)** concentrates on confirmation and consolidation of findings from Phase 1 using much larger numbers of samples to test whether proteins are differentially expressed for each candidate biomarker individually and in various combinations. Sample size estimates depend on the sample variance and desired detectable difference in expression. In previous proteomic studies on HCV-associated HCC described above, mean mass to charge ratios (m/z) of individual proteins detected ranged from approximately 3-25 with standard deviations of 1.3-14.[86, 87] The vast majority, however, have ranged between 2-5 with standard deviations of 2-4. Thus, at the lower range of variance, a sample size of 30 per group would provide 80% power to detect a 1.5-fold difference in protein expression with $\alpha < 0.05$. At the higher range of variance, 113 samples per group would be required to provide the same level of power. These estimates are in keeping with the experience of Drs [name] & [name] and from the wider clinical proteomics literature. In general, 50-100 specimens are required to estimate sensitivity and generate initial specificity estimates in clinical proteomics experiments. In the context of our study, we have planned to study 50-100 subjects per fibrosis stage, in both mono-infected and co-infected subjects (200-400 total

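### The 30 and 113 per group are sized for an absolute shift of 1.5 units at an unstated mean of 3, so the stated 80% power does not hold for a 1.5-fold difference in general

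*Protocol*

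**What the plan says.** Protocol section VIII, Justification for sample size, reports values from earlier proteomic studies: "The vast majority, however, have ranged between 2-5 with standard deviations of 2-4". From these it concludes that, at the lower end of variance, "a sample size of 30 per group would provide 80% power to detect a 1.5-fold difference in protein expression", with alpha below 0.05, and that at the higher end "113 samples per group would be required to provide the same level of power". It does not give the reference mean, the test, the scale of the SD, the group the SD belongs to, or whether the SD rises with the mean.

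The planned Phase 2 size is 50-100 per fibrosis stage in each infection group. On allocation, the validation paragraph says "Ideally, equal numbers of patients will be studied in each of these groups". The discovery paragraph plans "In addition to simple across-group and across-category comparisons (ANOVA), correlations between the degree of fibrosis" and peak intensities by Spearman rank, without naming a scale for the ANOVA. The pilot results in section VII report peaks that were higher and peaks that were lower in advanced fibrosis.

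**The concern.** A fold change is a ratio. A power calculation for a ratio needs either a reference mean, to turn the ratio into a difference, or a variability measure on the ratio (log) scale. The protocol gives neither. It quotes means from 2 to 5, over which a 1.5-fold increase is anything from 1.0 to 2.5 units, and pairs the ratio with one raw SD.

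That SD is about as large as the mean. A normal model with mean 3 puts 7% of values below zero at SD 2 and 23% at SD 4, which does not suit a peak intensity. A spread that grows with the mean is therefore at least plausible, and the calculation does not address it.

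At stake is what a reader can take from the printed 80%: which 1.5-fold markers Phase 2 would find, and whether a negative result for a peak means much.

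**Working it through.** **Inputs (protocol, Justification for sample size).** Alpha 0.05, power 80%, effect 1.5-fold, SD 2 or 4, means mostly 2-5, stated n 30 and 113, planned n 50-100. Equal groups come from the validation paragraph. Two-sided testing is assumed, because one-sided gives 22 and 88 and does not reproduce the figures. The quoted means and SDs are printed as mass-to-charge ratios; they are read here as peak intensities, which the expression comparison requires.

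**1. Reproducing the plan.** n per group = 2(1.960 + 0.842)² SD²/Δ² = 15.70 SD²/Δ².
- SD 2, Δ 1.5: 15.70 × 4/2.25 = 27.9; by t-test 28.9, so 29 (stated 30).
- SD 4, Δ 1.5: 15.70 × 16/2.25 = 111.6; by t-test 112.6, so 113 (stated 113).

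Power at the stated n is 81% and 80%. A difference of 1.5 is a 1.5-fold increase only when 0.5 × mean = 1.5, that is, at a mean of 3.

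**2. Same model, other means in the quoted range.** Constant SD, Δ = 0.5 × mean, t-test n for 80%:

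| Lower mean | Δ | n, SD 2 | n, SD 4 |
|---|---|---|---|
| 2 | 1.0 | 64 | 253 |
| 3 | 1.5 | 29 | 113 |
| 4 | 2.0 | 17 | 64 |
| 5 | 2.5 | 12 | 42 |

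**3. A decrease from the same reference.** 3/1.5 = 2, so Δ = 1.0. The standardised effect is 1.0/2 = 0.50 or 1.0/4 = 0.25. Power is 48% at n = 30 and 46% at n = 113; 80% needs 64 and 253.

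**4. If the SD scales with the mean (3 against 4.5).** The result depends on which group the quoted SD describes.
- *Mean-3 group.* Root-mean-square SD = SD × √((1 + 1.5²)/2) = 2.55 or 5.10. Power by t-test is 61% (n = 30) and 60% (n = 113). Simulated lognormal and gamma intensities give 61-66%. About 47 and 183 per group are needed.
- *Pooled.* The root-mean-square SD is 2 or 4 as printed. Power is about 80-85%.
- *Higher-mean group.* Root-mean-square SD = SD × √((1 + 1/1.5²)/2) = 1.70 or 3.40. Power is about 91-94%.

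Under the first reading, a decrease from 3 to 2 has the same power as an increase, because both means and SDs are rescaled by the same factor.

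**5. Power at the planned sizes (t-test).** The last column treats the two infection groups as combined.

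| Case | n = 50 | n = 100 | n = 200 |
|---|---|---|---|
| SD 2, increase, constant SD | 96% | >99% | >99% |
| SD 2, decrease, constant SD | 70% | 94% | >99% |
| SD 2, SD scales from the mean-3 group | 83% | 99% | >99% |
| SD 4, increase, constant SD | 46% | 75% | 96% |
| SD 4, decrease, constant SD | 24% | 42% | 70% |
| SD 4, SD scales from the mean-3 group | 31% | 54% | 84% |

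Simulation of the third row gives 85-86% at n = 50.

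**6. Effect and SD both on the log scale.** For lognormal intensities, log-SD = √ln(1 + CV²). CV 2/3 gives 0.606 and CV 4/3 gives 1.011. With ln 1.5 = 0.405, the standardised effects are 0.669 and 0.401, and the t-test needs 37 and 99 per group. At these settings power at n = 30 is 72% and at n = 113 is 85%. The gain depends on shape: for gamma intensities with SD 4 and n = 100, a log-scale t-test has about 30% power against about 56% on the raw scale.

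**The case against.** **The loss is not a fact of the document.** A reader might infer that true power at the stated n is 60-66%. That needs two assumptions the protocol does not make: that the SD is proportional to the mean, and that the quoted SD belongs to the lower-mean group. Under the other two readings in step 4 the loss vanishes or reverses. This objection stands, so 60-66% is one case in a range. It does not rescue the printed claim, because the mismatch in steps 1-3 needs no such assumption.

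**The decrease is a matter of labelling.** A marker falling from 4.5 to 3 has the same power as one rising from 3 to 4.5. That is correct. It confirms that the printed figure belongs to one pair of means, which the protocol does not name.

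**The raw-scale ANOVA is inferred.** A reader might conclude that the planned ANOVA uses raw intensities and loses power. The protocol names no scale for it. The averaging step ("Intensity values for each peak will be averaged for each duplicate sample pair analyzed") is described for the classification-tree input, and a transformation is ordinary SAP content. Spearman correlations, classification trees and single-marker AUROCs do not change under a monotone transformation of intensity. This objection stands in full.

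**The planned n is not 30, and groups are combined.** At the lower variance, 50-100 per group is mostly adequate. The primary accuracy analyses combine the infection groups, so a stage may hold up to 200. The protocol itself says 113 are needed at the higher variance, above its planned maximum of 100, and it calls these figures estimates. All of that limits the consequence. It does not correct the sentence, and comparisons within and between infection groups are also planned.

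**Conclusion.** The point holds as an error in the stated power. The figures 30 and 113 give 80% power for a common-SD comparison of mean 3 with mean 4.5, not for a 1.5-fold difference in general. With the plan's own constant SD, a decrease from 3 to 2 has 48% and 46% power at those sizes. If the SD scales with the mean, power lies between about 60-66% and 91-94%, depending on which group the quoted SD describes, and the protocol does not say.

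The documents do not support a claim that the study as a whole is underpowered for this reason. At SD 2, the planned 50 per group gives about 85% with a scaling SD. The weak spot there is a decrease with constant SD, at 70% with 50 per group and 94% with 100. At SD 4 power is low at 50-100 per group in most cases, but part of that gap is already disclosed by the stated need for 113.

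Nor do the documents support requiring a log-scale or rank analysis. Which scale is better depends on the intensity distribution, which is not given.

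These results rest on two-sided alpha 0.05 for a single peak, a reference mean of 3 as implied by the stated n, and equal groups.

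**What to change.** In Justification for sample size, do one of the following:

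- Restate the detectable effect as an absolute difference of 1.5 intensity units at a reference mean of 3, with a common SD of 2 or 4, and drop the general fold-change wording.
- Put effect and variability on the same log scale, state the distributional assumption, and replace 30 and 113 with the matching figures (about 37 and 99 per group under lognormal intensities at mean 3).

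Under either option, say which group the quoted SD describes and whether it is taken to rise with the mean. Also give the power at 50 and 100 per group for an increase and a decrease at both variances, as in the step 5 table.

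The cost is a few sentences and a small table; no change to recruitment or analysis follows from it. The first option narrows the claim to one reference mean. The second raises the lower-variance figure from 30 to about 37 and commits the protocol to a distributional assumption that should be checked against Phase 1 intensities.

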Biomarker Discovery for HIV–HCV Most biomarker programs focus on a single disease. Our attempt to define serum biomarkers associated with progression of liver disease in HIV–HCV co-infection is quite novel. However, it will likely be complicated by the intrinsic variability of the two underlying conditions and the varied therapeutic interventions used. Although the SELDI TOF MS platform is ideally suited to this type of complex situation, we will still need to exercise great care in selecting both patients and controls (see below). The stages of any biomarker program are Discovery, Validation and Identification. We will approach this complex problem in three general Phases.

Phase 1: Our initial **Discovery** effort will focus on otherwise ‘healthy’ HCV mono-infected controls and HIV-HCV co-infected patients with preserved CD4 cell counts (>350 cell/ul) and suppressed HIV RNA (< 50 copies/ml for at least 6 months on stable HIV treatment). Both groups will have evidence of replicating HCV (RT-PCR RNA+). Patients with other causes of liver disease or co-morbidities (i.e., current alcohol or drug use, Hepatitis B, TB) or prior/current HCV treatment will be excluded. This strategy should minimize potential “noise” in the serum proteome arising due to HIV-related immunosuppression and comorbidities (see detailed patient selection methods below).

Phase 2: Validation studies will be conducted with the groups above but in greater numbers (50-100 per fibrosis category) to confirm the validity of candidate biomarkers and guide prioritization efforts for biomarker **Identification** (see Sample Size Justification below). As samples accrue in our CIHR-funded archive, we will also have the opportunity to apply SELDI analysis to small numbers of serial samples from individual patients (e.g., with repeated biopsies). These sample sets may provide further validation of candidate biomarkers and/or biomarker patterns.

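### The stated Phase 2 total of 200-400 samples is half of the 400-800 that the plan's own per-cell numbers require, and the feasibility statement does not settle which is meant

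*Protocol*

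**What the plan says.** All references are to the protocol.

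- **VI. Methods, Phase 2** says validation will use the Phase 1 groups "in greater numbers (50-100 per fibrosis category"). It does not say whether the number applies to each infection group or to both together.
- **VIII. Research Plan, SELDI Data Analysis–Validation** names four categories, "minimal fibrosis (F0-1), mild fibrosis (F2), moderate fibrosis (F3), severe fibrosis/cirrhosis (F4"), and sets "n = 50-100 per fibrosis category and infection group". Equal numbers per group are described as the ideal, and stages may be regrouped if scores turn out to be unevenly distributed.
- **VIII. Research Plan, Justification for sample size** plans "50-100 subjects per fibrosis stage, in both mono-infected and co-infected subjects (200-400 total" samples). It gives 30 per group at the lower range of variance and 113 at the higher, for 80% power to detect a 1.5-fold difference at alpha 0.05. Most means are put at 2-5 and most standard deviations at 2-4.
- **VIII. Research Plan, Feasibility** expects 150-200 eligible co-infected subjects and about 175 biopsies a year in the mono-infection clinics, to be used retrospectively and prospectively. It concludes that "the number of samples we require represents about 40% of available patients".
- **VIII. Research Plan, General Data Analyses** pools the two infection groups by level of fibrosis for the primary analyses and then repeats them for each group separately.

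**The concern.** The validation section and the sample size section describe the same phase, and their totals differ by a factor of two. The 200-400 figure is reached only by leaving out one factor of two that the validation section fixes: the infection groups are pooled, or one group's total is labelled as the overall total, or four categories become two.

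The number per cell (fibrosis category by infection group) is what specific aim 3 rests on, since that aim compares co-infected and mono-infected subjects at similar stages. The validation section also compares peaks within and between infection groups. Assay workload and the number of controls to recruit change by the same factor of two.

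**Working it through.** **1. The authors' counting convention.** Phase 1 studies 10 "sera per fibrosis category and diagnostic group (total= 40 patients"). Two extremes of fibrosis and two infection groups give 10 x 2 x 2 = 40, so the stated total is reproduced when both factors are counted.

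**2. The same convention in Phase 2.** Inputs: 4 categories, 2 infection groups, 50-100 per cell (validation section).

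- Lower end: 4 x 2 x 50 = 400
- Upper end: 4 x 2 x 100 = 800
- Per infection group: 4 x 50 = 200 to 4 x 100 = 400

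The stated 200-400 is not reproduced. Three variants do give it: 4 x 50-100 with infection groups pooled, 4 x 50-100 within one infection group, and 2 regrouped stages x 2 groups x 50-100.

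**3. Number per cell and per pooled stage.**

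| Total | Per cell (total / 8) | Per stage, groups pooled (total / 4) |
|---|---|---|
| 200-400 | 25-50 | 50-100 |
| 400-800 | 50-100 | 100-200 |

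**4. Power per cell.** The test is a two-sample t-test, two-sided alpha 0.05, with effect size (0.5 x mean) / SD for a 1.5-fold difference. The plan's own figures come first. A mean of 3 gives a difference of 1.5. For 80% power that needs 29 per group at SD 2 (plan: 30) and 113 at SD 4 (plan: 113). The mean of 3 is therefore inferred; the plan states only 2-5. The table gives power at mean 3, with the range over means 2 to 5 in brackets.

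| n per cell | SD 2 | SD 4 |
|---|---|---|
| 25 | 74% (41 to 99%) | 26% (14 to 58%) |
| 50 | 96% (70 to >99%) | 46% (24 to 87%) |
| 100 | >99% (94 to >99%) | 75% (42 to 99%) |

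At 25 per cell the number is also below the plan's own low-variance figure of 30 per group.

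**5. Co-infected availability.** The 400-800 design needs 200-400 co-infected patients; 150-200 are expected.

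- Minimum: 200/200 = 100% to 200/150 = 133%
- Maximum: 400/200 = 200% to 400/150 = 267%

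**6. The 40% statement.** The denominator is not given. As an assumption, take both groups combined, with 150-200 co-infected plus 175 mono-infected per year and no retrospective cases.

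| Years of biopsies | Pool | 200 needed | 400 needed | 800 needed |
|---|---|---|---|---|
| 1 | 325-375 | 53-62% | 107-123% | 213-246% |
| 2 | 500-550 | 36-40% | 73-80% | 145-160% |
| 3 | 675-725 | 28-30% | 55-59% | 110-119% |

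Forty per cent of the three-year pool is 270-290 samples, inside the stated 200-400. Against the minimum of the 400-800 design, the lowest share in the table is 55%.

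**The case against.** Several points on the other side have force.

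- **The primary analysis is pooled.** A reader might infer that the main analysis could be left with 25 per group. The documents do not support that. With infection groups combined, even a total of 200 leaves 50 per stage, above the plan's figure of 30. The loss falls on the stratified and between-group comparisons. This limits the consequence but does not remove the contradiction, because aim 3 depends on those comparisons.
- **The 40% may be right.** A reader might infer that it is false, or true only at the bottom of the range. Without a denominator neither can be shown. It fits 200 of a two-year combined pool of 500, or 270-290 of a three-year pool. If it refers to controls alone, 200 of three years' biopsies is 200/525 = 38%. Retrospective cases enlarge the pool by an unstated number.
- **The mono-infected arm may be recruitable.** A reader might infer a shortage of controls, or of F4 patients in particular. That would require a recruitment window the plan does not state and a stage distribution borrowed from a co-infected series. The plan also allows recruitment at other centres if numbers fall short (Strengths and Limitations).
- **Stages may be regrouped.** Two stages by two groups would give 200-400. The plan offers regrouping only as a response to uneven scores, and the design it states has four categories.

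**Conclusion.** The contradiction stands: the validation section implies 400-800 samples, and the sample size section states 200-400. It rests on multiplication alone and needs no outside assumption. The Phase 1 total shows that the authors count both factors elsewhere.

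The consequence is a two-fold uncertainty in the number per cell for comparisons by stage and infection group. The power figures depend on the inferred mean of 3, but at any mean from 2 to 5 power at SD 4 is low with 25 per cell.

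On feasibility, two statements are secure. The 400-800 design takes the whole upper estimate of eligible co-infected patients even at its minimum. The 40% cannot be checked as written, and 400 samples would exceed it on a combined pool of up to three years of biopsies without retrospective cases. Three full years is generous for prospective recruitment, since the timeline places the Phase 2 assays in year three.

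**What to change.** Use one figure in VI. Methods (Phase 2) and in the validation, sample size and feasibility text of VIII. Research Plan. There are two ways to do this.

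1. State 400-800 in total, 200-400 per infection group. Correct the feasibility paragraph accordingly, including the shortfall of co-infected patients against the 150-200 expected.
2. Keep 200-400 in total. Change the validation section to 25-50 per fibrosis category and infection group, and state the lower power this gives for comparisons stratified by infection group.

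In either case, give the numerator, the denominator and the recruitment period behind the 40%, separately for co-infected and mono-infected subjects and with the expected retrospective cases counted. State the mean used in the sample size calculation as well, so that the 30 and 113 can be reproduced.

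The cost is wording only. The price is that either the stated feasibility (option 1) or the stated stratified power (option 2) becomes less favourable.
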